8. STATISTICAL METHODS AND DETERMINATION OF SAMPLE SIZE STATISTICAL AND ANALYTICAL PLANS

8.1 General Considerations for Data Analysis

The methodology presented in this section represents a brief overview of the statistical methods that will be fully detailed in the statistical analysis plan (SAP). The SAP will be finalized before the database is locked and unblinded. Any changes to the methods described in the final SAP will be described and justified in the clinical study report.

Study sites will be pooled into analysis centers for the efficacy analyses. The composition of pooled analysis centers will be finalized before the database is locked and unblinded.

All statistical analyses will be performed using SAS statistical software (Version 9.2 or above). Statistical significance will be tested at the 2-sided 5% level. Subgroup analyses (eg, prior biologic use) may be performed.

Data collected in this study will be presented using summary tables, figures, and subject data listings. Summary tables will present data by treatment group and, if applicable, by time of collection. Continuous variables will be summarized using descriptive statistics, specifically the mean, median, standard deviation, minimum and maximum. Categorical variables will be summarized by frequencies and percentages. Figures will be used to support the presentation of certain data.

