#### **6. RANDOMIZATION**

IWRS will be used for randomization. The randomization scheme will be reviewed and approved by a member of the sponsor's Biostatistics and Data Management (BDM) group or designee. The sites will randomize eligible subjects by contacting IWRS at Visit 2 after all the relevant Baseline

procedures are completed and assessed as appropriate. A subject who fulfills the study eligibility requirements will be randomly assigned to treatment. The randomization will be stratified by prior biologic use.

The IWRS will assign a randomization number to the subject, which will be used to link the subject to the treatment group and will specify a unique Blister Wallet IP kit number for the IP to be dispensed to the subject at Visit 2 for the Titration Period. The sites will log in to IWRS during each subsequent subject visit to obtain the kit numbers of the Bottle Kits to be dispensed at study Visits 3-7.

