## 12.8 Efficacy Analyses

### 12.8.1 Primary Efficacy Analyses

For each of the co-primary efficacy endpoints, proportion of subjects who achieved PASI-75 and IGA success at Week 24, will be tested to compare the difference between the subjects treated with PPC-06 and placebo, separately. To provide sufficient evidence of treatment effect, both PASI and

IGA based response rate must be rejected at the same significance level. The hypothesis testing for the three dose groups will be conducted sequentially from high to low dose; therefore, the 2-sided Type I error rate remains at the 0.05 level.

The primary efficacy analyses will be based on the FAS population using MI. Each multiple imputed dataset will be analyzed using a logistic regression model with treatment group, baseline BMI, and pooled analysis center as factors. The primary treatment comparisons will be the contrasts between the PPC-06 doses and placebo. The estimates and standard errors (SEs) of the log (odds ratio) based on the 50 imputed datasets will be combined by applying Rubin's rules for multiple imputed datasets. The combined log (odds ratio), odds ratio and associated 95% CI, and the resulting p-value will be provided. SAS Proc MI, Proc LOGISTIC, and Proc MIANALYZE will be utilized for these analyses. The averaged proportion of PASI-75 responders and IGA Success Rates over the 50 imputed datasets will also be presented.

Sensitivity analyses will be conducted using m-NRI and LOCF, following a same method as described above for each multiple imputed dataset. For each of the co-primary efficacy endpoints, proportion of subjects who achieved PASI-75 and IGA success at Week 24, will be tested to compare the difference between the subjects treated with PPC-06 and placebo, separately. PASI-75 and IGA Success Rates will be analyzed using a logistic regression model with treatment group, baseline BMI, and pooled analysis center as factors. The odds ratio between each PPC-06 group and placebo, along with the 95% CI and p-value will be reported.

Supporting analysis of the primary endpoints will also be performed using m-NRI based on the PP population.

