### **12.8.4 Subgroup Analyses**

The co-primary efficacy endpoints will be analyzed for the following subgroups:

- Baseline hsCRP (< 5 mg/L, >=5 mg/L)
- Baseline BMI (<30, >=30)
- Occurrence of diarrhea (Subjects reported diarrhea as adverse event by Week 24, subject did not report diarrhea by Week 24)

The same method as described in [Section 12.8.1](#) will be used for the subgroup analyses, except that no formal hypothesis testing will be performed.

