14.2.1.3.2	Analysis of Co-Primary Efficacy Outcome, Subgroup Analysis, PASI-75 Response Rate at Week 24 by Baseline BMI, Full Analysis Set, Multiple Imputation
14.2.1.3.3	Analysis of Co-Primary Efficacy Outcome, Subgroup Analysis, PASI-75 Response Rate at Week 24 by Occurrence of Diarrhea, Full Analysis Set, Multiple Imputation
14.2.1.4.1	Analysis of Co-Primary Efficacy Outcome, Subgroup Analysis, IGA Treatment Success Rate at Week 24 by Baseline hsCRP (mg/L), Full Analysis Set, Multiple Imputation
14.2.1.4.2	Analysis of Co-Primary Efficacy Outcome, Subgroup Analysis, IGA Treatment Success Rate at Week 24 by Baseline BMI, Full Analysis Set, Multiple Imputation
14.2.1.4.3	Analysis of Co-Primary Efficacy Outcome, Subgroup Analysis, IGA Treatment Success at Week 24 by Occurrence of Diarrhea, Full Analysis Set, Multiple Imputation
14.2.1.5.1	Analysis of Co-Primary Efficacy Outcome, PASI-75 Response Rate at Week 24 by Visit and Analysis Sites, Full Analysis Set, Multiple Imputation
14.2.1.5.2	Analysis of Co-Primary Efficacy Outcome, IGA Treatment Success at Week 24 by Visit and Analysis Sites, Full Analysis Set, Multiple Imputation
14.2.2	Summary of Secondary Efficacy Tables
14.2.2.1.1.1	Analysis of Secondary Efficacy Outcome - Change from Baseline in Total PASI Score by Visit, Double-Blind Treatment Period, Full Analysis Set, Multiple Imputation
14.2.2.1.1.2	Analysis of Secondary Efficacy Outcome - Percent Change from Baseline in Total PASI Score by Visit, Double-Blind Treatment Period, Full Analysis Set, Multiple Imputation

14.2.2.1.2.1	Analysis of Secondary Efficacy Outcome - Change from Baseline in Total PASI Score by Visit, Double-Blind Treatment Period, Full Analysis Set, LOCF
14.2.2.1.2.2	Analysis of Secondary Efficacy Outcome - Percent Change from Baseline in Total PASI Score by Visit, Double-Blind Treatment Period, Full Analysis Set, LOCF
14.2.2.1.3.1	Analysis of Secondary Efficacy Outcome - Change from Baseline in Total PASI Score by Visit, Double-Blind Treatment Period, Full Analysis Set, OC
14.2.2.1.3.2	Analysis of Secondary Efficacy Outcome - Percent Change from Baseline in Total PASI Score by Visit, Double-Blind Treatment Period, Full Analysis Set, OC
14.2.2.1.4.1	Analysis of Secondary Efficacy Outcome - Change from Baseline in Total PASI Score by Visit, Double-Blind Treatment Period, PP Population, OC

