Odds Ratio	X.XX	X.XX	X.XX	
Odds Ratio 95% CI	X.XX, X.XX	X.XX, X.XX	X.XX, X.XX	
p-value [3]	X.XXXX	X.XXXX	X.XXXX	

Note: PASI=Psoriasis Area and Severity Index; SE=Standard Error; CI=Confidence Interval. PASI-75 Response is defined as achieving a reduction of 75% or greater from Baseline in the Psoriasis Area and Severity Index (PASI-75) at the end of Week 24.

[1] Average PASI-75 response rate over 50 imputed datasets.

[2] Logistic model includes treatment group, baseline BMI, and pooled analysis center as factors.

[3] p-value is for null hypothesis that the combined log (Odds Ratio) equals 0.

Generated on XX/XX/XX:XXXX by XXXXX / Uses: XXXX / Reference: Listings XXXX

<Repeat for>

Table 14.2.1.3.2: Analysis of Co-Primary Efficacy Outcome, Subgroup Analysis  
PASI-75 Response Rate at Week 24 by Baseline BMI  
Full Analysis Set, Multiple Imputation  
[Baseline BMI < 30kg/m^2] [Baseline BMI >= 30kg/m^2]

Table 14.2.1.3.3: Analysis of Co-Primary Efficacy Outcome, Subgroup Analysis  
PASI-75 Response Rate at Week 24 by Occurrence of Diarrhea  
Full Analysis Set, Multiple Imputation  
[Subjects Reporting any Diarrhea by Week 24] [Subjects Not Reporting any Diarrhea by Week 24]

Table 14.2.1.4.1: Analysis of Co-Primary Efficacy Outcome, Subgroup Analysis  
IGA Treatment Success Rate at Week 24 by Baseline hsCRP (mg/L)  
Full Analysis Set, Multiple Imputation  
[Baseline hsCRP < 5mg/L] [Baseline hsCRP >= 5mg/L]

*Programming note: modify the Note accordingly for the definition of IGA treatment success*

Table 14.2.1.4.2: Analysis of Co-Primary Efficacy Outcome, Subgroup Analysis  
IGA Treatment Success Rate at Week 24 by Baseline BMI  
Full Analysis Set, Multiple Imputation  
[Baseline BMI < 30kg/m^2] [Baseline BMI >= 30kg/m^2]

*Programming note: modify the Note accordingly for the definition of IGA treatment success*

Table 14.2.1.4.3: Analysis of Co-Primary Efficacy Outcome, Subgroup Analysis  
IGA Treatment Success at Week 24 by Occurrence of Diarrhea  
Full Analysis Set, Multiple Imputation  
[Subjects Reporting any Diarrhea by Week 24] [Subjects Not Reporting any Diarrhea by Week 24]

*Programming note: modify the Note accordingly for the definition of IGA treatment success*

Table 14.2.1.5.1: Analysis of Co-Primary Efficacy Outcome  
PASI-75 Response Rate at Week 24 by Visit and Analysis Sites  
Full Analysis Set, Multiple Imputation

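### Two planned subgroup tables compare PPC-06 with placebo within strata defined by on-study diarrhoea, a treatment-affected post-randomisation event, so their odds ratios are not randomised comparisons

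*SAP*

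**What the plan says.** SAP 12.8.4 names three subgroups for PASI-75 and IGA success at Week 24: "Baseline hsCRP (< 5 mg/L, >=5 mg/L"), baseline BMI split at 30, and "Occurrence of diarrhea (Subjects reported diarrhea as adverse event by Week 24, subject did not report diarrhea by Week 24"). It says that the method of SAP 12.8.1 "will be used for the subgroup analyses, except that no formal hypothesis testing will be performed". That method is multiple imputation followed by a treatment contrast: "Each multiple imputed dataset will be analyzed using a logistic regression model with treatment group, baseline BMI, and pooled analysis center as factors".

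The table list in SAP 16 carries the plan through, for example "PASI-75 Response Rate at Week 24 by Occurrence of Diarrhea, Full Analysis Set, Multiple Imputation" (Table 14.2.1.3.3, with 14.2.1.4.3 for IGA). The shell labels the strata "Subjects Reporting any Diarrhea by Week 24] [Subjects Not Reporting any Diarrhea by Week 24". That shell is Table 14.2.1.3.1, repeated for the other subgroup tables. For each dose against placebo it prints a log odds ratio with standard error, an odds ratio, a 95% confidence interval and a p-value.

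On prior biologic use, SAP 6 says "The randomization will be stratified by prior biologic use", and Protocol 8.1 says "Subgroup analyses (eg, prior biologic use) may be performed". It does not appear among the SAP 12.8.4 subgroups or in the SAP 16 table list.

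**The concern.** A subgroup comparison inherits the protection of randomisation only if membership is fixed before treatment starts, or at least cannot be changed by treatment. Baseline hsCRP and BMI meet that condition. Diarrhoea reported by Week 24 does not. If the drug causes extra diarrhoea, the active-arm reporters are those who would have had it anyway plus those in whom the drug provoked it. The placebo reporters are only the first kind. The non-reporters differ correspondingly. Any link between the tendency to get diarrhoea and the tendency to respond then appears as a difference between drug and placebo.

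Diarrhoea is also unlikely to be neutral for the Week 24 outcome. Protocol 6.3 allows dose reduction or interruption for gastrointestinal intolerance, and the synopsis gives unresolved gastrointestinal intolerability as an example of a reason for early termination.

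At stake is how two tables are read. They could suggest that efficacy does, or does not, depend on gastrointestinal tolerability, and they cannot support either statement. Dropping formal tests would not remove selection bias from the point estimates.

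**Working it through.** **Timing.** Protocol 6.2 puts the first dose on Day 1, the day after the Baseline Visit at which subjects are randomised. The notes to Protocol Table 1-1 start adverse event collection after the first dose. Membership of the diarrhoea strata is therefore always settled after randomisation. Protocol 7.5.1.4 lists diarrhoea among the events commonly seen with PPC-06, so treatment can be expected to affect membership.

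**Planning figures.** The plan gives no figure for this subgroup. Its sample-size inputs (SAP 7) are 15% response on placebo, 45% on PPC-06, 100 randomised and about 50 completers per arm, two-sided 0.05. They reproduce its stated power:

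- z = (0.30 − 1.96 × √(2 × 0.30 × 0.70 / 50)) / √((0.15 × 0.85 + 0.45 × 0.55) / 50) = (0.300 − 0.180) / 0.0866 = 1.39, giving 0.918 per endpoint.
- For two endpoints taken as independent, 0.918² = 0.842, which matches the stated 84%.

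The 15% and the 100 per arm are reused below.

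**Can a null drug show an effect within these strata?** All rates here except the 15% are assumptions. Let response average 15% in both arms, so the drug has no effect on anyone. Half of patients respond less often than the other half: 10% against 20%, or 5% against 25%. Placebo diarrhoea is 10% in both halves. The excess on active falls only on the half less likely to respond.

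Worked case, 40% diarrhoea on active, 10% against 20%:

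- Diarrhoea in the less responsive half is 0.10 + (0.40 − 0.10)/0.5 = 0.70.
- Active reporters: (0.35 × 0.10 + 0.05 × 0.20)/0.40 = 0.1125. Odds ratio against placebo at 0.15: (0.1125/0.8875)/(0.15/0.85) = 0.72.
- Active non-reporters: (0.15 × 0.10 + 0.45 × 0.20)/0.60 = 0.175. Odds ratio 1.20.

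| Diarrhoea on active | Reporters (10% v 20%) | Non-reporters (10% v 20%) | Reporters (5% v 25%) | Non-reporters (5% v 25%) |
|---|---|---|---|---|
| 20% | 0.81 | 1.05 | 0.63 | 1.10 |
| 30% | 0.75 | 1.11 | 0.52 | 1.23 |
| 40% | 0.72 | 1.20 | 0.46 | 1.42 |
| 50% | 0.70 | 1.33 | 0.43 | 1.69 |

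The true odds ratio is 1 throughout. If the excess fell instead on the likelier responders, the direction would reverse. In the worked case, reporters become (0.05 × 0.10 + 0.35 × 0.20)/0.40 = 0.1875, odds ratio 1.31. If diarrhoea and response were unrelated, there would be no bias.

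**Precision in the placebo reporter stratum.** Expected responders = 100 × rate × 0.15; chance of none = 0.85^n.

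| Placebo diarrhoea (assumed) | Placebo subjects | Expected responders | Chance of no responder |
|---|---|---|---|
| 5% | 5 | 0.75 | 0.44 |
| 10% | 10 | 1.50 | 0.20 |
| 15% | 15 | 2.25 | 0.09 |

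**Prior biologic use for comparison.** Protocol 5.3 caps prior users at 30%, so at most about 30 per arm, with 30 × 0.15 = 4.5 expected placebo responders. If 10% are prior users (assumption), the figures are 10 subjects and 1.5 responders. This subgroup is also imprecise, but each stratum is a randomised comparison.

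**The case against.** The strongest reply is that this is an exploratory Phase 2 output for which the SAP disclaims formal testing, and that asking whether response goes with gastrointestinal tolerability is reasonable. That limits the consequence: the co-primary analysis and the dose hierarchy are untouched. It does not rescue the contrast, because a biased estimate stays biased without a test, and the shells print p-values anyway.

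The size of the bias is open to challenge. The illustration assumes a particular link between diarrhoea and response, for which the documents give no evidence. It shows that a false effect difference is possible, not how large it would be here. Protocol 7.5.1.3 counts only Bristol Type 7 stool as diarrhoea, which makes any assumed rate less certain still.

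A reader might infer several stronger points that the documents do not support:

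- *The event is drug-caused.* Placebo subjects can report diarrhoea too; treatment-affected is the accurate term.
- *The model cannot be fitted.* At 10 placebo reporters the chance of no placebo responder is 0.20 in a completed data set. One model covers all arms, so active subjects also inform the BMI and centre terms, and the number of pooled centres is not given. Very imprecise is as far as this goes.
- *A subject must stay on study to be a reporter.* Adverse events are also recorded at the early termination visit, so someone who leaves because of diarrhoea can be counted.
- *The SAP breaks the protocol by omitting prior biologic use.* Protocol 8.1 gives it as an optional example, and stratified randomisation does not oblige a subgroup analysis.

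**Conclusion.** The point holds as a moderate one. Tables 14.2.1.3.3 and 14.2.1.4.3 would report PPC-06 versus placebo odds ratios that are not randomised comparisons and that can show effect differences under a null drug effect. This follows from the timing of the event and its known relation to treatment, and needs no assumed rate. How far the estimates would depart from the truth cannot be determined from the documents. The imprecision rests on an assumed 5% to 15% placebo diarrhoea rate and the planned 15% response.

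Separately, the p-values in the shared shell do not fit the statement in SAP 12.8.4 that there is no formal testing. That mismatch covers the hsCRP, BMI and diarrhoea tables alike. Adding prior biologic use is a recommendation, not the correction of a contradiction. A reader might take all this as a threat to the trial's main conclusion; it is not, since the co-primary type I error is unaffected.

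**What to change.** Before unblinding:

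1. In Tables 14.2.1.3.3 and 14.2.1.4.3, remove the drug-placebo log odds ratio, odds ratio, confidence interval and p-value. Show the number of subjects and response rate by diarrhoea status within each arm, labelled as descriptive. Amend SAP 12.8.4 to match.
2. Add prior biologic use (yes/no, as recorded at randomisation) as a baseline subgroup for both endpoints, with a note that the user stratum is at most about 30 per arm and its estimates will be imprecise.
3. Remove the p-value row and its footnote from all subgroup shells (hsCRP, BMI and diarrhoea, for PASI-75 and IGA), so that they agree with SAP 12.8.4.

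The cost is a short SAP amendment and shell edits: two tables simplified, two added, and one row dropped from the shared shell. Prior biologic use is already recorded as the stratification factor, so no new data and no change to the sample size are needed.

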## 11. DATA CONVENTIONS FOR ANALYSIS

### 11.1 General Statistical Principles

All statistical tests will be performed at the unadjusted 0.05 (two-sided) level of significance.

All observed and derived variables (e.g., change from baseline, percentage change from baseline, response status) used in the summaries of analyses will be presented in by-subject listings. Descriptive statistics will be used to provide an overview of the efficacy and safety results. For categorical parameters, the number and percentage of subjects in each category will be presented. The denominator for percentage will be based on the number of subjects appropriate for the purpose of analysis. For continuous parameters, descriptive statistics will include number of subjects, mean, standard deviation (SD), median, minimum, and maximum.

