Generated on XX/XX/XX:XXXX by XXXXX / Uses: XXXX / Reference: Listings XXXX

Table 14.2.1.2.2: Analysis of Co-Primary Efficacy Outcome  
IGA Treatment Success Rate at Week 24  
PP Population, m-NRI

	PPC-06 400 mg QD (N=XX)	PPC-06 400 mg BID (N=XX)	PPC-06 600 mg BID (N=XX)	Placebo (N=XX)
IGA Treatment Success Rate, n / N (%) [1]	XX / XX (XX.X)	XX / XX (XX.X)	XX / XX (XX.X)	XX / XX (XX.X)
Logistic Regression [2]				
Odds Ratio, PPC-06 vs. Placebo	X.XX	X.XX	X.XX	
Odds Ratio 95% CI	X.XX, X.XX	X.XX, X.XX	X.XX, X.XX	
p-value	0.XXXX	0.XXXX	0.XXXX	
Pairwise Comparisons Between PPC-06 Treatments				
Odds Ratio, PPC-06 vs. PPC-06 600 mg BID	X.XX	X.XX		
Odds Ratio 95% CI	X.XX, X.XX	X.XX, X.XX		
p-value	0.XXXX	0.XXXX		
Odds Ratio, PPC-06 vs. PPC-06 400 mg BID	X.XX			
Odds Ratio 95% CI	X.XX, X.XX			
p-value	0.XXXX			

Note: IGA= Investigator's Global Assessment; m-NRI=modified non-responder imputation; CI=Confidence Interval. IGA Treatment Success is defined as achieving an IGA score of clear or almost clear (IGA score 0 or 1) at the end of Week 24.

[1] n = Number of responders at Week 24. N = Number of subjects with a Week 24 assessment.

[2] Logistic model includes treatment group, baseline BMI, and pooled analysis center as factors.

Generated on XX/XX/XX:XXXX by XXXXX / Uses: XXXX / Reference: Listings XXXX

< Repeat Table 14.2.1.2.2 for >

Table 14.2.1.2.3: Analysis of Co-Primary Efficacy Outcome, Sensitivity Analysis  
IGA Treatment Success Rate at Week 24  
Full Analysis Set, m-NRI

Table 14.2.1.2.4: Analysis of Co-Primary Efficacy Outcome, Sensitivity Analysis  
IGA Treatment Success Rate at Week 24  
Full Analysis Set, LOCF

*Programming note: modify the Note accordingly for the definition of LOCF*

Table 14.2.1.2.5: Analysis of Co-Primary Efficacy Outcome, Sensitivity Analysis  
IGA Treatment Success Rate at Week 24  
Full Analysis Set, OC

*Programming note: modify the Note accordingly for the definition of OC*

Table 14.2.1.3.1: Analysis of Co-Primary Efficacy Outcome, Subgroup Analysis  
PASI-75 Response Rate at Week 24 by Baseline hsCRP  
Full Analysis Set, Multiple Imputation  
[Baseline hsCRP < 5mg/L][Baseline hsCRP >= 5mg/L]

	PPC-06 400 mg QD (N=XX)	PPC-06 400 mg BID (N=XX)	PPC-06 600 mg BID (N=XX)	Placebo (N=XX)
PASI-75 Response Rate				
N	XX	XX	XX	XX
Response Rate [1]	XX.X	XX.X	XX.X	XX.X
Logistic Regression [2]				
Log (Odds Ratio) (SE), PPC-06 vs. Placebo	X.XX (X.XX)	X.XX (X.XX)	X.XX (X.XX)	

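### Six subgroup table shells print 36 unlabelled p-values although SAP 12.8.4 excludes formal testing in subgroups, and no analysis compares the subgroup levels

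*SAP*

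**What the plan says.** SAP 12.8.4 opens with "The co-primary efficacy endpoints will be analyzed for the following subgroups" and lists three two-level factors: baseline hsCRP (cut at 5 mg/L), baseline BMI (cut at 30), and whether diarrhea was reported as an adverse event by Week 24. It applies the method of 12.8.1 "except that no formal hypothesis testing will be performed". Section 12.8.1 itself calls for a combined odds ratio, its 95% CI and a p-value.

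The shells in SAP section 16 keep that p-value. Table 14.2.1.3.1 is produced once per level (its title carries "Baseline hsCRP < 5mg/L][Baseline hsCRP >= 5mg/L") and has a p-value row with one entry per dose. Footnote [3] reads "p-value is for null hypothesis that the combined log (Odds Ratio) equals 0". The shell is repeated for BMI and diarrhea, and all three are repeated for IGA. The primary-analysis Tables 14.2.1.1.1 and 14.2.1.2.1 carry the same footnote.

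SAP 11.1 adds a general rule: "All statistical tests will be performed at the unadjusted 0.05 (two-sided) level of significance". No subgroup-specific label or adjustment is given, and no treatment-by-subgroup interaction is specified. The only mention of interaction terms is in Protocol 8.7.2, as an unspecified option for continuous secondary endpoints.

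**The concern.** The text and the shells give the programmer different instructions. The text can be read as removing the p-value that 12.8.1 would otherwise produce, while the shells require it.

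The layout also invites a known misreading. Each level is judged against placebo on its own and nothing sets the two levels side by side. A subgroup holds only part of the sample, so even with an identical drug effect in both levels, one may cross 0.05 and the other may not. A reader could then conclude that the drug works only in, say, subjects with BMI below 30. At stake is the interpretation of the subgroup tables, not the primary conclusion.

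**Working it through.** **Inputs.** From SAP 12.8.4: three factors, two levels each, two co-primary endpoints. From SAP 3: three doses and placebo, 1:1:1:1. From SAP 7: response 15% on placebo and 45% on drug, 100 randomized and about 50 completers per arm, power at least 84%. From SAP 11.1: two-sided 0.05. The documents give no expected subgroup split, so splits are assumptions.

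**1. The plan's own power figure.** For n per arm,

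Power(n) = Φ{[Δ − 1.96·√(2p̄q̄/n)] / √[(p₀q₀ + p₁q₁)/n]},

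with Δ = 0.30, p̄ = 0.30, 2p̄q̄ = 0.42 and p₀q₀ + p₁q₁ = 0.1275 + 0.2475 = 0.375.

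At n = 50: (0.30 − 1.96 × 0.0917)/0.0866 = 1.39, so power is 0.918 for one endpoint. Treating the two endpoints as independent, 0.918² = 0.842. This reproduces the stated 84%.

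**2. Number of p-values.** 3 factors × 2 levels × 3 doses × 2 endpoints = 36. They form 18 level pairs, 12 of them for the two baseline factors (2 × 3 × 2).

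**3. Discordant pairs under a uniform effect.** Let a and b be the power in the two levels from the formula above. The levels contain different subjects, so

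P(exactly one level has p<0.05) = a(1 − b) + b(1 − a).

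| Subjects per arm in the two levels | a | b | Discordant |
|---|---|---|---|
| 25 / 25 (50 per arm) | 0.646 | 0.646 | 46% |
| 15 / 35 | 0.430 | 0.795 | 54% |
| 10 / 40 | 0.300 | 0.847 | 64% |
| 50 / 50 (100 per arm) | 0.918 | 0.918 | 15% |
| 30 / 70 | 0.729 | 0.979 | 28% |
| 20 / 80 | 0.546 | 0.989 | 46% |

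Simulation of the four-arm layout with a shared placebo arm, correlated endpoints and 50:50 splits gives 45–49% at 50 per arm and 14–16% at 100 per arm, in line with the formula.

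For the 12 baseline-factor pairs, the expected number of discordant pairs at equal splits is 12 × 0.457 = 5.5 at 50 per arm and 12 × 0.151 = 1.8 at 100 per arm. Dependence between pairs does not affect these expectations.

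The arithmetic assumes that the factor is independent of treatment. That is reasonable for hsCRP and BMI. It is not for diarrhea, which Protocol 7.5.1.4 lists among the events commonly seen with PPC-06 and which is recorded after randomization. The discordance figures should not be applied to that factor.

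**4. Precision of a direct comparison.** With 25 subjects per arm in each level and the planning rates in both, the unadjusted variance of one log odds ratio is 1/(25 × 0.1275) + 1/(25 × 0.2475) = 0.475. For the ratio of two odds ratios it is 2 × 0.475 = 0.951, SE 0.975. The 95% CI runs from the estimate divided by exp(1.96 × 0.975) = 6.8 to the estimate multiplied by 6.8. With 50 per arm in each level the SE is √0.475 = 0.689 and the factor is exp(1.96 × 0.689) = 3.9.

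**The case against.** The strongest defence is that 12.8.4 imports the 12.8.1 output whole, p-value included, and that the word formal only denies it confirmatory status. On that view the p-values are nominal, and the general rule in 11.1 does not override the specific one. The shells are a proposed outline, and footnote [3] looks carried over from the primary tables. This is plausible as to how the mismatch arose, but it does not remove it. Neither 12.8.4 nor the shells say nominal or exploratory, and the footnote presents these p-values just as the primary ones are presented.

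A second objection is that a 95% CI in each level permits the same level-by-level reading, so deleting p-values is not enough. That stands, and it is why a direct comparison of levels is worth adding. It is also fair that this comparison will be imprecise (step 4) and that 12.8.4 does not claim to assess effect modification.

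Two stronger readings are tempting and not supported:

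- **That 36 unadjusted tests inflate the trial's 5% error rate.** The protected level belongs to the high-to-low dose sequence in 12.8.1, which requires both endpoints to reject for a dose. The subgroup outputs stand outside it. The chance of some p<0.05 among the 36 when the drug does nothing is therefore not comparable with 5%. It would count either endpoint in either direction, and it varies widely with the test used.
- **That the tables will show false effect modification.** Discordant p-values are a likely risk under a uniform effect, not a certain result. The plan contains no rule for interpreting them.

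**Conclusion.** The mismatch is real and the count of 36 is exact. Co-primary type I error and power are unaffected. The harm is interpretive: for hsCRP and BMI, a uniform 15% against 45% effect gives one level below 0.05 and the other above in about 45–49% of pairs at 50 per arm and about 15% at 100 per arm, rising to 64% and 46% at the most unequal splits examined.

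These figures rest on assumed splits and on unadjusted two-group tests. They do not come from the planned BMI- and centre-adjusted logistic model pooled over 50 imputations. The 50-per-arm case takes completers only; the 100-per-arm case treats every randomized subject as fully informative. The point should be corrected, but it does not threaten the primary analysis.

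**What to change.** 1. Delete the p-value row and footnote [3] from Tables 14.2.1.3.1–14.2.1.3.3 and 14.2.1.4.1–14.2.1.4.3, so that they follow 12.8.4. Keep the odds ratios with 95% CIs and label them exploratory.
2. For baseline hsCRP and BMI only, add one line per dose with the treatment-by-subgroup ratio of odds ratios and its 95% CI, from the same logistic model with an interaction term and pooled over imputations. Note in the SAP that it will be imprecise.
3. State in 12.8.4 and on the two diarrhea tables that this subgroup is defined after randomization, so comparisons within its levels are descriptive only.

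The cost is six edited shells, one interaction term in existing code and a sentence or two of text. No additional data are needed and nothing changes for subjects.
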